7.3.2 Enrollment /Baseline

Enrollment/Baseline Visit (Visit 1, Day 0)

- Obtain demographic information, medical history, medication history, alcohol and tobacco use history.
- Record Concomitant Medications.
- Record vital signs, results of physical examination, other assessments.
- Collect blood/urine for:
 - Hematology: CBC - hemoglobin, hematocrit, white blood cells (WBC) with differential count, platelet count
 - Biochemistry: CMP - glucose, calcium, albumin, total protein, sodium, potassium, CO₂, chloride, BUN, creatinine, total bilirubin, alanine aminotransferase (ALT), aspartate aminotransferase (AST), alkaline phosphatase (ALP), lactate dehydrogenase (LDH)
 - Urinalysis: UA with microscopic evaluation
 - Serum pregnancy test: done within 24 hours prior to Investigational Product administration, and results must be available prior to Investigational Product administration
 - 40 mL of blood will be collected for research purposes in the laboratory of [name], including immune response baseline evaluation.
- Where feasible, as determined by PI, research study biopsy for histology and/or immune response assays may be collected at the screening visit or the baseline visit.
- Administer the Investigational Product.
- Assessment and recording of ECOG Performance Status
- Assessment and recording of Tumor Burden (lesion measurements)
- Observation and recording of adverse or serious adverse events as defined by CTCAE v5.0

7.3.3 Optional Study Visits (for multiple dose cycle only)

(Week 4 Day 28 +/- 7 business days)

- Record vital signs, results of physical examination, other assessments
- Collect blood/urine for:
 - Hematology: CBC - hemoglobin, hematocrit, white blood cells (WBC) with differential count, platelet count; blood clotting tests: prothrombin time (PT), activated partial thromboplastin time (aPTT)
 - Biochemistry: CMP - glucose, calcium, albumin, total protein, sodium, potassium, CO₂, chloride, BUN, creatinine, total bilirubin, alanine aminotransferase (ALT), aspartate aminotransferase (AST), alkaline phosphatase (ALP), lactate dehydrogenase (LDH); thyroid tests: (TSH and FT4)
 - Urinalysis: UA with microscopic evaluation
 - Serum pregnancy test: done within 24 hours prior to Investigational Product administration, and results must be available prior to Investigational Product administration
 - 40 mL of blood will be collected for research purposes in the laboratory of [name], including immune response evaluation.
- Optional research study biopsy for histology and immune response assays may be collected.
- Administer the Investigational Product.
- Assessment and recording of ECOG Performance Status
- Assessment and recording of Tumor Burden (lesion measurements)
- Assessment and recording of Concomitant Medications
- Observation and recording of adverse or serious adverse events as defined by CTCAE v5.0
- CT as clinically indicated and/or PET scan (photographs may be utilized for melanoma confined to the skin)

(Week 7 Day 49 +/- 7 business days)

- Record vital signs, results of physical examination, other assessments
- Collect blood/urine for:
 - Hematology: CBC - hemoglobin, hematocrit, white blood cells (WBC) with differential count, platelet count
 - Biochemistry: CMP - glucose, calcium, albumin, total protein, sodium, potassium, CO₂, chloride, BUN, creatinine, total bilirubin, alanine aminotransferase (ALT), aspartate aminotransferase (AST), alkaline phosphatase (ALP), lactate dehydrogenase (LDH)
 - Urinalysis: UA with microscopic evaluation
 - Serum pregnancy test: done within 24 hours prior to Investigational Product administration, and results must be available prior to Investigational Product administration
 - 40 mL of blood will be collected for research purposes in the laboratory of [name], including immune response evaluation.
- Optional research study biopsy for histology and immune response assays may be collected.
- Administer the Investigational Product.
- Assessment and recording of ECOG Performance Status
- Assessment and recording of Tumor Burden (lesion measurements)
- Assessment and recording of Concomitant Medications

- Observation and recording of adverse or serious adverse events as defined by CTCAE v5.0

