The trial will be conducted in accordance with the ICH E6, the Code of Federal Regulations on the Protection of Human Subjects (45 CFR Part 46). The Principal Investigator will assure that no deviation from, or changes to the protocol will take place without prior agreement from the sponsor and documented approval from the Institutional Review Board (IRB), except where necessary to eliminate an immediate hazard(s) to the trial participants. All personnel involved in the conduct of this study have completed Human Subjects Protection Training.

I agree to ensure that all staff members involved in the conduct of this study are informed about their obligations in meeting the above commitments.

Principal Investigator: _____

[figure not shown]
Signature: _____ Date: _____

PROTOCOL SUMMARY

Title	Phase 1 Study Using a Plasmid DNA Coding for Emm55 Streptococcal Antigen in Patients with Unresectable Stage III or Stage IV Cutaneous Melanoma
Short Title	pDNA Intralesional Cancer Vaccine for Cutaneous Melanoma
Protocol Number	Melanoma 2017-01
Phase	Phase 1
Methodology	Non-randomized, open-label, uncontrolled
Study Duration	Approximately 1 year
Study Center(s)	Single-center
Objectives	Primary: To assess safety and feasibility Secondary: To assess any antitumor response
Number of Subjects	Six
Diagnosis and Main Inclusion Criteria	Male or female, confirmed stage III or stage IV unresectable melanoma with lesions accessible for intralesional injection
Study Product, Dose, Route, Regimen	Plasmid DNA encoding a Streptococcal antigen in a cationic polymer-based solution in doses of 100 µg delivered intralesionally at a single time point “Week 0” with a maximum of three lesions injected. The primary endpoint (DLT) will be assessed at 4 weeks.
Optional dosing	After primary endpoint has been met (DLT), at the investigator’s discretion in consultation with the sponsor, patients may receive additional doses on a 3-week cycle.
Follow-up - Primary	Week 4; Day 28+/-7 business days.
Follow-up – Optional.	21 days +/- 7 business days from last dose administered.
Follow-up – Long-term	Obtain OS/subsequent treatments for melanoma after MCC 19500 as of 11/16/2020 for all patients with clinical response if available.

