Study Procedures	
Six patients will receive IFx-Hu2.0 on an outpatient basis at a single time point in a single lesion, two lesions, or three lesions, as a monotherapy (a maximum of three lesions could be injected). These patients will be assessed for any immediate adverse reactions and at Week 4 (Day 28+/-7 business days) for any delayed adverse events.
 
After the primary endpoint has been met (DLT), patients may receive additional doses on an optional 3-week cycle.

Duration of Administration	Single time point with option for additional doses
Potential Risks	Other cancer vaccine trial results have reported patients experiencing reactions such as mild fever, skin reactions, sweats and chills, which are often described as “flu-like” symptoms.
Reference Therapy	None

Statistical Methodology	The data analysis is described to assess the safety of the injection of the study agent in six patients. The intention-to-treat approach will be used for response to treatment data analysis of this trial (secondary objective). The exploratory testing will be mainly descriptive in this pilot set of patients
--------------------------------	---

SCHEMATIC OF STUDY DESIGN

Note: If patient consents to additional treatment, this may be performed every three weeks with a 21-day follow-up visit.

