Enrollees will receive IFx-Hu2.0 at a single time point. Depending on the number of accessible lesions, a patient could receive up to three doses across three lesions (one dose per lesion). Forty milliliters of peripheral blood will be collected from these patients prior to treatment administration and at the follow-up visit four weeks later. The target dose will be 100 µg of plasmid DNA per lesion injected at a final dose volume of 200 µL per lesion. To allow for the observation of any acute toxicity in the first subject enrolled and prevent any occurrence of excessive toxicities in subsequent subjects, the first subject enrolled will receive a single dose of IFx-Hu2.0. Subsequent subjects will be administered the product after at least seven days. Beyond the first subject, the maximum number of lesions to be injected at any given time point in the study phase proposed is three lesions. These samples will be used to perform complete blood counts (CBC) and clinical chemistry tests. A urine sample will be obtained for urinalysis for protein and blood at the same frequency. Blood samples will be drawn for immune response evaluation as well. Peripheral blood collections, and where feasible, as determined by PI, tumor biopsies may be obtained on the first and subsequent treatment cycles. At the end of the study period a biopsy of the lesion injected and a non-injected lesion (if applicable) will be collected. At the discretion of the PI in consultation with the Sponsor, the patient will have the option of continuing the study at three-week intervals so long as the subject under study has not progressed.

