6.1.7 Starting Dose and Dose Escalation Schedule

The dose/lesion treated will be constant through this study: 100 µg of plasmid DNA per lesion injected at a final dose volume of 0.2 mL. However, depending on the subject, one, two, or three lesions would be injected at a time.

The subjects will receive IFx-Hu2.0 at a single time point as a monotherapy. These patients will then be observed for any dose-limiting toxicity or adverse events for up to four weeks. The maximum number of lesions to be injected in this study is three lesions.

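### The two-sided visit windows for the optional doses are not reconciled with the four-week DLT period or the three-week cycle

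*Combined protocol and SAP*

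**What the plan says.** **Dosing visits.** For patients on the multiple-dose cycle, Section 7.3.3 lists two visits, "Week 4 Day 28 +/- 7 business days" and "Week 7 Day 49 +/- 7 business days". At both, one of the listed actions is "Administer the Investigational Product". Both days are counted from Day 0, the day of the first dose. The footnote to the multiple-dose table in Section 7.3.7 repeats the two-sided window.

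**DLT period and gate.** Section 10.5 counts DLTs over four weeks. Section 6.1.7 says of the single time point: "These patients will then be observed for any dose-limiting toxicity or adverse events for up to four weeks". Section 7.1.2 describes a four-week assessment, after which patients move on to other care. The Protocol Summary and Section 6.1.9 allow more doses only after the DLT endpoint, at the investigator's discretion in consultation with the sponsor. No calendar day is attached to that condition. The Protocol Summary says the endpoint is assessed at 4 weeks, but sets the primary follow-up visit at "Week 4; Day 28+/-7 business days".

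**Delays.** Section 6.1.8 allows visits to slip by up to 7 business days. It does not mention early dosing.

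**Spacing.** The note under the design schematic reads: "If patient consents to additional treatment, this may be performed every three weeks with a 21-day follow-up visit". Section 4.1 says "the patient will have the option of continuing the study at three-week intervals so long as the subject under study has not progressed". Sections 6.1.9 and 7.1.2 also give a three-week cycle. None of them calls three weeks a minimum. The optional follow-up visit, by contrast, is timed from the preceding dose: "21 days +/- 7 business days from last dose administered".

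**The concern.** A visit tolerance that is harmless for a blood draw has a different effect when product is given at that visit. The minus side of the Week 4 window reaches back into the DLT period, and the text that should prevent early re-dosing does not name a day.

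Two things are at stake. The first is patient safety: in a six-patient trial whose primary aim is the safety of one treatment time point, a patient could be re-dosed before the planned observation is complete. The second is attribution: a serious event between an early dose 2 and Day 28 would follow two treatments, so it would be harder to read as toxicity of the single time point.

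The spacing of doses 2 and 3 is a lesser issue. Because dose 3 is anchored to Day 0 and not to dose 2, a late dose 2 shortens the interval unless the site also moves dose 3.

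**Working it through.** **Inputs.** Day 28 and Day 49, each with a window of 7 business days either side (Sections 7.3.3 and 7.3.7); a 28-day DLT period (Section 10.5); a delay of up to 7 business days (Section 6.1.8); a three-week cycle (Sections 4.1, 6.1.9 and 7.1.2). Assumptions: business days are Monday to Friday, there are no public holidays, and Day 0 is a weekday. Holidays would widen the windows.

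**Step 1: the plan's own figure.** With 0 DLTs in 6 patients, the one-sided 95% exact upper limit is 1 − 0.05^(1/6) = 0.393, as Section 10.5 states. It depends only on the number of patients and the DLT count, so the visit windows do not enter it.

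**Step 2: limits of the windows.** Example with Day 0 on a Monday: Day 28 is a Monday, five business days earlier is Day 21, and two more give Friday Day 18 and Thursday Day 17. All weekday starts:

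| Day 0 | Dose 2 window | Dose 3 window | DLT days left at earliest dose 2 |
|---|---|---|---|
| Mon | 17 to 37 | 38 to 58 | 28 − 17 = 11 |
| Tue | 17 to 37 | 38 to 58 | 11 |
| Wed | 19 to 37 | 40 to 58 | 28 − 19 = 9 |
| Thu | 19 to 39 | 40 to 60 | 9 |
| Fri | 19 to 39 | 40 to 60 | 9 |

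The unobserved part of the DLT period at the earliest dose 2 is therefore 9/28 = 32% to 11/28 = 39%.

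**Step 3: does the gate close this?** Further doses must follow the DLT endpoint, and a DLT is counted over four weeks. Read together with the four-week assessment in Section 7.1.2, that points to no dose 2 before Day 28. On the other side, the gate names no day, the assessment visit has the same two-sided window, and Section 7.3.3 gives product at the Week 4 visit. A site could hold the assessment and dose on Day 17 to 19 and stay inside both visit windows.

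**Step 4: dose 2 to dose 3.** Suppose dose 2 is delayed and dose 3 is kept on nominal Day 49. The gap in days is 49 minus the day of dose 2:

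| Day 0 | Delay of 1, 2, 3, 4, 5, 6, 7 business days |
|---|---|
| Mon | 20, 19, 18, 17, 14, 13, 12 |
| Tue | 20, 19, 18, 15, 14, 13, 12 |
| Wed | 20, 19, 16, 15, 14, 13, 12 |
| Thu | 20, 17, 16, 15, 14, 13, 10 |
| Fri | 18, 17, 16, 15, 14, 11, 10 |

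At the full permitted delay the gap is 10 to 12 days. Only a dose 2 on or before Day 28 leaves at least 21 days to Day 49.

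**Step 5: can both texts be met?** Day 49 is exactly three weeks after Day 28, so the Week 7 window is the Week 4 window moved by 21 days. For all 15 permitted dose 2 dates (7 before, the nominal day, 7 after), the date 21 days later lies inside the Week 7 window. A site can always keep the three-week cycle; the visit schedule does not oblige it to.

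**Step 6: with the fix.** Dose 2 falls on Day 28 to Day 37 or 39. Dose 3 falls 21 days later plus up to 7 business days (9 to 11 calendar days), so the gap is 21 to 32 days. Dose 3 is on Day 49 at the earliest. Its latest day is Day 67 for a Monday start and Day 69 for the others.

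**The case against.** The best reply is that a visit tolerance does not override a dosing condition. The DLT gate, the four-week assessment in Section 7.1.2 and the four-week DLT definition all point to a floor at Day 28, and the section on dose timing (6.1.8) speaks only of delays. This largely stands. A reader might infer that the protocol authorises re-dosing inside the DLT period; the documents do not support that. They contain a window that allows it and a gate that, on its natural reading, forbids it. What remains is that the operational visit list carries the minus side and nothing states which text prevails.

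On spacing, the reply is that a three-week cycle appears in several places, that the multiple-dose table is labelled a sample schedule, and that the short gap arises only if a site holds to Day 49 and disregards the cycle. That also stands. Taking the latest dose 2 and the earliest dose 3 would suggest gaps of 1 to 3 days, but that reading ignores the stated cycle altogether. The remaining point is that no sentence makes 21 days a minimum.

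On consequence, Section 10.5 ties a DLT to the agent and not to a particular dose, so a definitely related event of grade 3 or above after an early dose 2 but before Day 28 would still count. Onset times are recorded (Section 8.3), each optional dose needs investigator discretion and sponsor consultation, and the halting rule and medical monitor review apply (Sections 8.5 and 8.6). It would be too strong to say that such an event could not be attributed at all, or that the DLT analysis fails. Attribution to the single time point would be less clean, and that is the extent of it.

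**Conclusion.** The concern holds as an unreconciled conflict between the visit windows and the dosing rules. By the window alone, dose 2 may come on Day 17 to 19, with 9 to 11 of 28 DLT days to run; the gate points the other way without naming a day. The lack of a stated minimum between doses 2 and 3 is secondary, with a gap of 10 to 12 days in the worked example.

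These are limits of the schedule, not estimates of how often they would be reached; the documents give no basis for a frequency. They rest on Monday-to-Friday business days without holidays. The number of patients, the DLT counting rule and the 0.393 bound do not change. The documents also give no evidence that a shorter interval is hazardous. The case for change is caution and clean attribution in a first safety study. I rate it between minor and should-fix: a cheap improvement.

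**What to change.** For multiple-dose patients, amend Section 7.3.3, the multiple-dose footnote in Section 7.3.7, the primary follow-up row of the Protocol Summary and Section 6.1.9, so that all four agree:

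1. Dose 2 is given no earlier than Day 28 and only after the four-week DLT assessment is complete. Delay only, up to 7 business days. When the Week 4 assessment doubles as the dose 2 visit, it takes the same one-sided window.
2. Each later dose is given at least 21 days after the previous dose. Delay only, up to 7 business days. The visit is counted from the previous dose, as the optional follow-up visit already is.

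The single-dose window in Section 7.3.4 can stay for this purpose, since no product is given at that visit.

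**Cost.** Wording in four places and no extra patients. Optional doses can no longer be given early, and dose 3 may fall as late as Day 67 to 69 instead of Day 58 to 60. A patient who decides to continue only after an early Week 4 visit would need one dosing visit on or after Day 28. Booking the Week 4 visit of likely continuers from Day 28 onward avoids that.

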7.3.4 Final Study Visit

(Week 4 Day 28 +/- 7 business days for Single Dose Cycle)

OR

(Week 21 +/- 7 business after the last dose for Multiple Dose Cycle)

- Record vital signs, results of physical examination
- Collect blood/urine for:
 - Hematology: CBC - hemoglobin, hematocrit, white blood cells (WBC) with differential count, platelet count; blood clotting tests: prothrombin time (PT), activated partial thromboplastin time (aPTT)
 - Biochemistry: CMP - glucose, calcium, albumin, total protein, sodium, potassium, CO₂, chloride, BUN, creatinine, total bilirubin, alanine aminotransferase (ALT), aspartate aminotransferase (AST), alkaline phosphatase (ALP), lactate dehydrogenase (LDH); thyroid tests: (TSH and FT4)
 - Urinalysis: UA with microscopic evaluation
 - Serum pregnancy test
 - Anti-double-stranded DNA (anti-dsDNA) antibody test
 - Anti-DNase B Titer, Serum
 - 40 mL of blood will be collected for research purposes in the laboratory of [name], including immune response evaluation.
- Tumor sample biopsy of injected lesion for histology and immune response assays
- Biopsy of non-target lesion (if applicable)
- Assessment and recording of ECOG Performance Status
- Assessment and recording of Tumor Burden (lesion measurements)
- Assessment and recording of Concomitant Medications
- Observation and recording of adverse or serious adverse events as defined by CTCAE v5.0
- CT as clinically indicated and/or PET scan (photographs may be utilized for melanoma confined to the skin)

Overall Survival Status: Long Term Follow-up

- On 11/16/2020 (\pm 4 weeks), the survival status and subsequent anti-cancer therapy since last being seen on trial will be obtained from the EMR. Subsequent therapies will be documented from the EMR for melanoma (immune-based therapy, chemotherapy, radiation, surgery) with clinical response if available.

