6.1.8 Dose Adjustments/Modifications/Delays

No dose adjustments or modifications will be part of this study phase. However, the protocol will allow for delays of up to 7 business days to accommodate participant clinic visit rescheduling due to any unforeseen circumstances.

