7.1.2 Standard-of-care Study Procedures

Subjects will receive IFx-Hu2.0 as a monotherapy at a single time point and will be assessed for a period of four weeks. Once the four-week period expires and the toxicity/safety assessments have been completed, these patients will transition into standard-of-care or clinical trial protocols as determined by the PI and the clinical team. If the patient comes off study, PFS will need to be censored, but the time to first progression will be obtained during subsequent follow-up with the patient's consent. If the patient has a response to therapy, the patient will have the option of continuing the study at three-week intervals at the discretion of the PI in consultation with the Sponsor. In this setting, PFS will be measured in the traditional way. Where feasible, as determined by PI, tumor biopsies and peripheral blood collections may be obtained on subsequent treatment cycles.

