7.3.7 Schedule of Events Table

Schedule of Events Table

Schedule of Events: (Single dose cycle scenario)

Procedure	Screening (Day -36 to -1)	Week 0 (D=0)	Week 4** (D=28)*	Unscheduled visit	Early Termination Visit	Long-term Follow-up ¹
Informed consent eligibility	X					X
Physical exam w/vitals	X	X	X	X	X	
Medical history	X			X	X	X
Concomitant meds.	X	X	X	X	X	
AEs/SAEs	X	X	X	X	X	
IFx-Hu2.0 dosing		X				
Blood for Immune Response Evaluation		X	X	X	X	
***Clinical labs						
CBC, CMP	X	X	X	X	X	
LDH	X	X	X	X	X	
Blood clotting tests (PT/PTT)	X		X		X	
HLA typing (if not previously reported)		X				
EBV ab	X					
Hepatitis B and C, HTLV-1 & 2	X					
HIV, RPR (FTA if necessary)	X					
Thyroid Tests (Free T4, TSH)	X		X		X	
Serum Pregnancy Test	X	X	X		X	
Immunodeficiency Panel	X					
Urinalysis	X	X	X	X	X	
Anti-double-stranded DNA (anti-dsDNA)	X		X		X	
Anti-DNAse B Titer Serum	X		X		X	

ECG	X					
Optional Tumor sample/biopsies for immune response assays	X	X	X	X	X	
Optional Tumor sample/biopsies for histology	X		X	X	X	
CT and/or PET scan (Photographs may be utilized for melanoma confined to the skin)	X		X		X	
Performance Status	X	X	X	X	X	
Tumor Burden (lesion measurements)	X	X	X	X	X	
Confirmation of histology by Moffitt (may use archival tissue)	X					
Overall Survival						X

* +/-7 business days; **Final study visit; ***Screening labs may be performed within 7 days of treatment.

¹A long-term follow-up on 11/16/2020 (\pm 4 weeks) that includes the survival status and subsequent anti-cancer therapy since last being seen on trial will be obtained from the EMR. Subsequent therapies will be documented from the EMR for melanoma (immune-based therapy, chemotherapy, radiation, surgery) with clinical response if available.

Schedule of Events: (optional multiple dose cycle scenario, sample schedule for 3 cycles)

Procedure	Screening (Day -36 to -1)	Week 0 (D=0)	Week 4 (D=28)*	Week 7 (D=49)*	visit (21 days after last dose)	Unscheduled Visit	Early Term Visit	Long-term Follow-up ¹
Informed consent Eligibility	X							X
Physical exam w/vitals	X	X	X	X	X	X	X	
Medical history	X					X	X	X
Concomitant meds.	X	X	X	X	X	X	X	
AEs/SAEs	X	X	X	X	X	X	X	
IFx-Hu2.0 dosing		X	X	X				
Blood for Immune Response Evaluation		X	X	X	X	X	X	
***Clinical labs								
CBC, CMP	X	X	X	X	X	X	X	
LDH	X	X	X	X	X	X	X	
Blood clotting tests (PT/PTT)	X		X		X		X	
HLA typing (if not previously reported)	X							
EBV ab	X							
Hepatitis B and C, HTLV-1 & 2	X							
HIV, RPR (FTA if necessary)	X							

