8 ASSESSMENT OF SAFETY

8.1 Specification of Safety Parameters

This study will comply with all applicable regulations on IND safety reporting requirements to the FDA in accordance with 21 CFR 312.32. This study will utilize CTCAE v5.0 for toxicity and AE reporting. All appropriate treatment areas at Moffitt Cancer Center have access to a copy of the CTCAE v5.0. Careful evaluation to determine the toxicity of IFx-Hu2.0 as a monotherapy will be performed. Adverse events will be documented beginning at initiation of treatment (Day 0) and continue at each visit detailed in the study treatment schema until progression, loss to follow-up, withdrawal of consent, or death. Subjects with treatment-related toxicity will be followed for the ongoing drug-related adverse events until resolved, return to baseline, deemed irreversible by the Moffitt treating physician, or until the subject is lost to follow up, withdrawal of study consent, removal of the subject from the trial by the Moffitt treating physician, or start of a subsequent anti-cancer therapy.

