10.5 Sample Size

The intent of this study is to enroll six evaluable patients to assess the safety of IFx-Hu2.0 as a monotherapy. The sample size has the following precision for estimation of DLT rates for estimating ranging from 0.1 to 0.5. A DLT is defined as an adverse event equal to or greater than grade 3, definitely related to the investigational agent within a 4 week period. Precision is measured by 1-sided 95% upper confidence limit on the estimated DLT rate via exact binomial distribution. For example, if no DLT is observed in patients on IFX-Hu 2.0, then the true underlying DLT rate is lower than 0.393 with 95% confidence.

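### For single-dose patients the visit window lets the only scheduled post-dose safety visit fall on Day 17 or 19, before the 4-week DLT period ends

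*Combined protocol and SAP*

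**What the plan says.** Section 10.5 defines a DLT as an event of grade 3 or higher that is "definitely related to the investigational agent within a 4 week period". The Protocol Summary states "The primary endpoint (DLT) will be assessed at 4 weeks", and section 7.1.2 says that subjects "will be assessed for a period of four weeks". Feasibility (sections 4.2.1 and 10.4.1) means treating at least five of six patients without a DLT. Section 10.5 gives 0.393 as the one-sided 95% exact upper limit when no DLT is seen.

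The final visit in section 7.3.4 is "Week 4 Day 28 +/- 7 business days for Single Dose Cycle". The Protocol Summary has patients assessed "at Week 4 (Day 28+/-7 business days) for any delayed adverse events", and the single-dose schedule in section 7.3.7 prints the same window and marks Week 4 as the final study visit. That table has no other scheduled post-dose safety visit. Its remaining columns are unscheduled visits, early termination, and the record review around 11/16/2020, which collects survival, subsequent therapy and medical history.

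Section 6.1.8 describes the allowance only in one direction: "the protocol will allow for delays of up to 7 business days". Under section 8.1, AE documentation starts on Day 0 and is to "continue at each visit detailed in the study treatment schema until progression, loss to follow-up, withdrawal of consent, or death".

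**The concern.** The endpoint is defined over 28 days, but the visit that assesses it may take place well before Day 28 and still be within its window. For a single-dose patient no later contact is scheduled at which a new event would be asked about or a laboratory abnormality detected. The AE routines in sections 8.1 and 8.3 are built around visits.

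The 5-of-6 rule and the 0.393 limit are both statements about a 4-week DLT rate. They hold for that rate only if each counted patient's AE status is known through Day 28. A patient closed early counts as DLT-free on incomplete information, and with six patients each status carries weight.

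Two other gaps affect the same 28 days:

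- Section 8.1 ends documentation of new AEs at progression, while section 8.3 wants all AEs during the study recorded.
- Sections 5.3 and 10.5 aim for six evaluable patients, and sections 5.3 and 5.4.2 provide for replacements, but no section ties evaluability to 28 days of observation.

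Patients who take optional doses are asked about AEs again at a later visit, so for them the gap is covered. The smaller point there is that optional dosing is gated on the primary endpoint (section 6.1.9), yet the Week 4 dosing visit in section 7.3.3 carries the same minus window and does not say that the dose waits until Day 28.

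**Working it through.** **Inputs.** Window of Day 28 ± 7 business days (7.3.4); DLT period of 28 days (10.5); n = 6 and a one-sided 95% exact limit (10.5); pass if at most one DLT in six (4.2.1, 10.4.1). Assumed because the documents do not say: weekday dosing, no public holiday in the window, and the onset pattern of DLTs.

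**The plan's own figure.** With 0 of 6, the limit solves (1 − p)^6 = 0.05, so p = 1 − 0.05^(1/6) = 0.393. It reproduces, with all six patients fully observed.

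**Earliest in-window visit.** Day 28 falls on the same weekday as dosing. Counting back seven weekdays:

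- Monday or Tuesday dosing crosses two weekends: 11 calendar days back, Day 17. This leaves 11/28 = 39% of the period after the visit.
- Wednesday to Friday dosing crosses one weekend: 9 calendar days back, Day 19. This leaves 9/28 = 32%.

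**Effect on the two criteria.** Let k of six patients be seen at Day D, and let p be the true 4-week DLT rate. Under constant hazard, the chance that a DLT starts by Day D is q = 1 − (1 − p)^(D/28). If a share c of the later DLTs is still captured, the recorded rate for an early patient is q′ = q + c(p − q).

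- Upper limit with no DLT recorded: solve (1 − p)^(6−k) × (1 − q′)^k = 0.05. With c = 0 this is p = 1 − 0.05^(1/[(6 − k) + kD/28]).
- Pass chance: the probability of at most one recorded DLT, from 6 − k patients at rate p and k patients at rate q′.

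Example with D = 17, k = 1, c = 0: the exponent is 5 + 17/28 = 5.607, so the limit is 1 − 0.05^(1/5.607) = 0.414. At p = 1/3, q = 1 − (2/3)^(17/28) = 0.218. The pass chance is [(2/3)^5 + 5(1/3)(2/3)^4] × 0.782 + 0.218 × (2/3)^5 = 0.389.

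| Scenario (constant hazard) | Upper limit, no DLT recorded | Pass chance at p = 1/3 |
|---|---|---|
| All observed to Day 28, or all later DLTs captured | 0.393 | 0.351 |
| One at Day 17, half of later DLTs captured | 0.404 | 0.370 |
| One at Day 17, none captured | 0.414 | 0.389 |
| One at Day 19, none captured | 0.410 | 0.382 |
| Six at Day 17, half captured | 0.468 | 0.474 |
| Six at Day 17, none captured | 0.561 | 0.611 |
| Six at Day 19, none captured | 0.521 | 0.557 |

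At p = 0.20 with none captured, the pass chance goes from 0.655 to 0.685 (one at Day 17) or 0.830 (six at Day 17).

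**Sensitivity to the onset assumption.** With uniform onset, q = pD/28. With none captured and D = 17, the limits are 0.418 (one early) and 0.647 (six early; this is 0.393 × 28/17).

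**The case against.** A visit window is not the observation period. Section 7.1.2 releases patients only after the four weeks have expired and the assessments are done. Section 6.1.7 has them observed for up to four weeks, and section 10.4.4.1 counts treatment-emergent events to 30 days after the last dose. A DLT starting on Day 22 is therefore in scope, and what is missing is a way of finding it.

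Other routes may find it: unscheduled or early termination visits, spontaneous reporting, monitoring, and the later record review. Section 8.1 also follows ongoing treatment-related toxicity to resolution, subject to its stated stopping conditions, so a toxicity already present at the early visit that later worsens is covered. The definitely-related requirement makes late-onset events harder to count as DLTs in any case. Having all six patients at Day 17 is improbable: all would need Monday or Tuesday dosing and the earliest allowed visit. If 80% of later DLTs were captured (an assumption), one patient at Day 17 gives a limit of 0.397 and a pass chance of 0.359 at a true rate of 1/3; six give 0.421 and 0.398.

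Most of this stands as a limit on size. The gap is one of ascertainment, and only new-onset events after the visit are at risk. It does not close the gap. The sections on scope schedule no contact, and the other routes depend on the site becoming aware or on a retrospective record check. A symptom-free grade 3 laboratory change after Day 17 would have no scheduled test to reveal it. The one-directional wording in section 6.1.8 does not prove that the minus side is a mistake, since the symmetric window is printed consistently, but the plan states no reason for an early visit.

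**Conclusion.** The concern holds. Following the printed window, a single-dose patient can have the final safety visit 9 or 11 days before the DLT period ends, with no later AE contact scheduled. The possible bias runs only toward fewer recorded DLTs.

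The day count rests on weekday dosing without a holiday and is firm. The effect on the result is uncertain: it runs from none, through small with one early patient, to substantial only if many are seen early and later events stay unknown. Those figures depend on assumed onset patterns and capture rates. The loss is possible rather than certain, but it bears on the primary endpoint and is cheap to prevent, so it should be fixed. The points on progression, evaluability and optional dosing are secondary, and the conclusion does not depend on them.

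**What to change.** 1. In section 7.3.4, the Protocol Summary and the single-dose schedule, set the Week 4 visit at Day 28 with a window of 0 to +7 business days. Alternatively, keep the present window and require a telephone or chart AE check on or after Day 28 for anyone seen earlier.
2. In section 10.5, define a patient as evaluable for DLT if a DLT has occurred or AE status is known through Day 28.
3. In section 8.1, record AEs through Day 28 regardless of progression.
4. In section 7.3.3, state that no optional dose is given before Day 28, in line with the existing gate.

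The cost is a wording amendment, slightly less scheduling flexibility, and at most one call or chart check per patient seen early.
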